3.2. Endpoints

Primary Endpoints:

1. Frequency and severity of solicited injection site and systemic reactogenicity from time of study vaccine administration through Day 8 after each administration of study vaccine overall and by dosage group and pre-vaccination flavivirus immune status.
2. Frequency and severity of unsolicited vaccine-related adverse events (AE), including vaccine-related laboratory AE, from first administration of study vaccine until 28 days after the last vaccination overall and by dosage group and pre-vaccination flavivirus immune status.
3. Frequency, type, and duration of serious adverse events (SAE) and adverse events of special interest (AESI) considered related to study vaccine from the first administration of study vaccine until the end of the study overall, and by dosage group and pre-vaccination flavivirus immune status.
4. Frequency of new onset chronic medical conditions reported at any time from the first administration of study vaccine until the end of the study overall, and by dosage group and pre-vaccination flavivirus immune status.
5. Comparison of the frequency, type and duration of vaccine-related Grade 3 local, systemic, or laboratory AE, and Grade 2 or greater local or systemic reactogenicity through Day 8 after each

study vaccine administration between dosage groups and by pre-vaccination flavivirus immune status.

6. Comparison of study withdrawals and discontinuation of study vaccination due to any reason between dosage groups and by pre-vaccination flavivirus immune status.

Secondary Endpoints:

1. Frequency of seroconversion to ZIKV at each post-vaccination visit measured by ZIKV ELISA and neutralization assay in comparison with baseline samples (collected at Visit 00) overall, and by dosage group and pre-vaccination flavivirus immune status.
2. Per Visit GMT as measured by ZIKV ELISA and neutralization assay after each study vaccine administration and for each post-vaccination visit overall, and by dosage group and pre-vaccination flavivirus immune status.
3. Peak GMT as measured by ZIKV ELISA and neutralization assay after each vaccination and overall, and by dosage group and pre-vaccination flavivirus immune status.
4. Proportion of subjects with at least a 4-fold rise in ZIKV GMT as measured by ZIKV ELISA and neutralization assay at 4 weeks after each vaccination compared with baseline overall, and by dosage group and pre-vaccination flavivirus immune status.

Exploratory Endpoints:

1. Number and proportion of subjects who develop an acute febrile illness (AFI) or an acute rash illness (ARI) who have evidence of acute ZIKV or DENV infection detected within 14 days of symptom onset. This endpoint will be analyzed for all subjects overall, and by dosage group, product received, and pre-vaccination flavivirus immune status.
2. Number and severity of laboratory confirmed ZIKV and DENV infections during the study, overall, by treatment group, and pre-vaccination immune status, where severity is described by:
 - Duration of symptoms
 - Grade of symptoms (mild, moderate, severe)
 - Use of concomitant medications
 - Need for hospitalization or other medical care

Laboratory confirmation will be made by AFI or ARI with either: 1) evidence of acute ZIKV and DENV infection within 14 days of symptom onset or 2) a 4-fold rise in DENV or ZIKV neutralization titers between samples collected at the last visit prior to and at the first visit following the AFI/ARI, where available.

3.3. Study Definitions and Derived Variables

Baseline Values

Unless otherwise specified, baseline values will be defined as the last values obtained prior to the first investigational vaccination. Vital signs (pulse and blood pressure) assessed at screening will be considered as baseline. Any medical condition that is present at the time that the subject is screened will be considered as baseline and not reported as an adverse event.

Adverse Events of Special Interest

For this study, Neurologic and Neuroinflammatory Disorders will be considered as adverse events of special interest (AESI). These include Acute Disseminated Encephalomyelitis (ADEM, including site specific variants), Cranial Nerve Disorders (including paralyses/paresis), Guillain-Barre Syndrome (GBS, including Miller Fisher Syndrome and other variants), Immune-mediated Peripheral Neuropathies and Plexopathies, Optic Neuritis, Multiple Sclerosis, Narcolepsy, Transverse Myelitis, meningitis, or meningoencephalitis.

Baseline Flavivirus Immune Status

Subjects enrolled in the study will have blood drawn during the screening visit (Visit 00) or pre-vaccination at the first visit (Visit 01) to determine baseline flavivirus immune status. Serum will be tested via serology for antibodies to ZIKV and DENV. Baseline flavivirus immune status will be treated as a categorical variable and will be used to stratify tables and figures throughout the analyses specified in this SAP. The goal of determining the baseline flavivirus status is to see if there is an effect of baseline flavivirus seropositivity on response to ZPIV. With this in mind, subjects are categorized initially at ZIKV seropositive (based on a positive IgM or IgG assay pre-vaccination) or ZIKV seronegative (based on negative IgM and IgG tests pre-vaccination). Subjects are then subcategorized as DENV seropositive or seronegative, within each ZIKV category.

Baseline flavivirus immune status will be defined primarily as follows:

- ZIKV Seropositive: any subject with detectable ZIKV antibodies pre-vaccination
- ZIKV Seronegative: any subject without detectable ZIKV antibodies pre-vaccination

Baseline flavivirus immune status will then be further classified into the following groups:

- ZIKV Seropositive and DENV Seropositive
- ZIKV Seropositive and DENV Seronegative
- ZIKV Seronegative and DENV Seropositive
- ZIKV Seronegative and DENV Seronegative

Baseline DENV and ZIKV serostatus will be determined via IgM antibody and IgG ELISA assays, with subject results reported as either 'positive' or 'negative'. If a subject has a positive ZIKV result from either the IgM or IgG ELISA assays, they will be considered ZIKV seropositive at baseline. If a subject has inconclusive results for their baseline flavivirus immune status, they will not be included in analyses stratified by baseline flavivirus immune status but will be included in analyses of all subjects.

Post-Baseline Seropositivity

Seropositivity post-baseline is defined as a titer ≥ 10 and ≥ 100 for ZIKV MN50 and a titer ≥ 200 and ≥ 600 for ZIKV ELISA.

Seroconversion

Seroconversion for ZIKV MN50 titers and ZIKV ELISA titers is defined as ≥ 4 -fold rise from baseline.

Acute Febrile Illness and Acute Rash Illness

Acute febrile illness (AFI) is defined as grade 1 or higher fever on at least 2 consecutive days accompanied by any of the following: new rash not limited to vaccination site, arthralgia, or nonpurulent conjunctivitis. Acute rash illness (ARI) is defined as any new rash not limited to vaccination site.

Laboratory Confirmation of ZIKV or DENV Infection Among Those with AFI or ARI

Among subjects with AFI or ARI, laboratory confirmation of ZIKV or DENV infection will be made by either 1) evidence of acute ZIKV and DENV infection within 14 days of symptom onset (confirmed via PCR) or 2) a 4-fold rise in DENV or ZIKV neutralization titers between samples collected at the last visit prior to and at the first visit following the AFI/ARI illness visit, where available.

Consideration of ZIKV Microneutralization Assay Results in Analysis

The lower limit of quantitation (LLOQ) for ZIKV microneutralization assay results is 10. Any values less than the LLOQ will be assigned a value of 5 by the lab. This imputed value will be used for the purpose of calculating summary statistics such GMT and will be displayed in listings of immunogenicity data. If a subject has a baseline titer below the LLOQ (reported as 5), then they will be considered seroconverted if the post-baseline titer is at least 20 (at least a 4-fold rise). Similarly, a subject with a baseline ZIKV MN50 below the LLOQ will be considered seropositive if the post-baseline titer is at least 10 or 100, as applicable.

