Reactogenicity assessments will include an assessment of solicited adverse events occurring from the time of each study vaccination through Day 8 after each study vaccination, which includes an assessment of injection site reactions including pruritus (itching), erythema (redness), ecchymosis (bruising), induration (hardness)/swelling, pain, and tenderness as well as systemic reactions including fever, feverishness (chills/shivering/sweating), fatigue (tiredness), malaise (general unwell feeling), myalgia (body aches/muscular pain exclusive of the injection site), arthralgia (joint pain exclusive of the injection site), headache, rash, nausea, vomiting, diarrhea, and abdominal pain. All subjects will complete a subject memory aid from Day 1 through Day 8 after each study vaccination to record solicited injection site and systemic reactogenicity. Subject memory aids will be reviewed with the subjects by phone visit on Day 4 and at scheduled clinical visits on Days 2 and 8 after each study vaccination.

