### **8.2.2. Visit 02, Study Day 2, Day 2 Clinic Visit after First Vaccination**

- Obtain interim medical history, including an assessment for new medical conditions by interview of subjects and note any changes since the previous clinic or phone visit.
- Ask about febrile/rash illness. If the subject reports history of AFI/ARI within the past 14 days, conduct a febrile/rash illness Assessment and sample collection as per [Section 8.7](#).
- Collect information on all concomitant medications taken since last visit and record on the appropriate case report form.
- Perform a targeted physical examination, if indicated based on review of complete medical history.
- Obtain vital signs including oral temperature, blood pressure, and pulse.
- Review the Memory Aid with the subject.
- Examine vaccination site for local reactions.
- Collect blood samples for a CPT tube and a Paxgene tube
- Assess for unsolicited AEs, SAEs, AESIs, and new onset chronic medical conditions and record on the appropriate case report form.

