## **9.4 Type and Duration of Follow-up of Adverse Events**

Solicited injection site and systemic AEs (reactogenicity events) will be documented and reported from Day 1 through Day 8 after each study vaccination via memory aid, clinic visits on Day 2 and Day 8 after vaccination, and interview by telephone visit on Day 4 after each study vaccination.

Unsolicited AE will be documented from Day 1 through approximately 28 days after the last vaccination. Blood for safety laboratory tests will be collected on Day 8 and Day 15 after each study vaccination. All AEs will be assessed and followed through resolution or stabilization even if this extends beyond the study-reporting period.

AEs related to AFI/ARI will be collected and assessed from the time the ICF is signed through the end of the study, and followed until resolution or stabilization.

SAE, AESIs, and new-onset chronic medical conditions will be collected and assessed from the time of the first study vaccination through the end of the study, and followed until resolution or stabilization. Resolution of an AE and SAE is defined as the return to pretreatment status or stabilization of the condition with the expectation that it will remain chronic.

AFI and ARI will be collected after signing ICF through the end of the study.

Follow-up procedures, evaluations, and outcomes will be recorded on the appropriate case report form.

---

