## 11 STATISTICAL CONSIDERATIONS

### 11.1 Study Hypotheses:

The primary goal of this study is to assess and compare the safety and reactogenicity of a homologous prime boost regimen of ZPIV given at two different dose levels in a population living in a flavivirus/ZIKV endemic area. Secondary goals are to explore the humoral responses to ZIKV after each vaccination in subjects with and without pre-existing flavivirus/ZIKV immunity. Blood samples are also collected for measuring ZIKV-related cellular and humoral immunity and systems biology in future assays. Enhanced surveillance for febrile and rash illness after signing the ICF will be performed to obtain preliminary data on the incidence and clinical presentation of naturally occurring flavivirus infections after vaccination. This study, like other Phase I studies, is exploratory rather than confirmatory, and thus the objective is not to formally test any test hypotheses, though comparisons between vaccine and placebo and between dose levels will be made. In addition, comparisons will be stratified by pre-vaccination flavivirus immune status of the volunteer and outcomes of flavivirus-naïve and flavivirus immune volunteers will be compared.

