Venous blood and urine were collected from subjects on Day 8 and Day 15 following each vaccination for safety clinical laboratory tests. The tests include WBC, hemoglobin, hematocrit, and platelets, ALT, AST, total bilirubin, BUN, creatinine, and urine dipstick for protein and glucose. Laboratory values were assessed for adverse events according to the grading scale in [Table 7](#). Unsolicited adverse events were collected from all subjects through Day 57 (28 days after the 2nd vaccination). These events were assessed for severity and relatedness to study product. Serious adverse events (SAE), adverse events of special interest (AESI), and new onset chronic medical conditions (NOCMC) were collected for the duration of each subject's follow-up. Adverse events of special interest (AESI) for this study are neurologic and neuroinflammatory disorders collected through the duration of the subject's follow-up period.

Subjects were observed for development of an AFI/AI and all related adverse events from the time of signing the informed consent form through follow-up. Subjects who reported an ARI/AI were assessed for the following symptoms which are graded on a scale from 1 (least severe) to 3 (most severe): fever, feverishness, lethargy, restlessness, rash not at injection site, nonpurulent conjunctivitis, headache, shortness of breath, retino-orbital pain, myalgia, arthralgia, arthritis, nausea, abdominal pain, vomiting (evaluated for presence only), and bleeding (evaluated for presence only).

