9.9. Other Safety Measures

Summary tables of acute febrile illness (AFI) and acute rash illness (ARI) events will be presented. The percentage of subjects who develop ARI or AFI will be summarized by treatment group and baseline flavivirus status. Additionally, summary tables for AFI/ARI events will be presented by baseline flavivirus status.

Summaries of subjects reporting any events, any medically treated events, and any events requiring concomitant medication, including the total number of events and the number, percentage and exact 95% Clopper-Pearson CI of subjects reporting an event, will be presented for all subjects and by baseline flavivirus immune status in [Table 140](#), [Table 141](#), [Table 142](#), [Table 143](#), and [Table 144](#). Similar summaries presented by infection confirmation method are presented in [Table 147](#), [Table 148](#), [Table 149](#), [Table 150](#) and [Table 151](#).

Summaries of laboratory confirmed ZIKV and DENV infections are also presented. ZIKV and DENV infection is presented via two methods: subjects presenting with ARI/AFI and positive Arbovirus PCR result within 14 days of symptom onset or subjects presenting with ARI/AFI and a 4-fold rise in ZIKV or DENV titers following the onset of illness compared to prior to illness. The total number of laboratory confirmed ZIKV or DENV infections are summarized by treatment group, baseline flavivirus status, and confirmation method in [Table 154](#), [Table 155](#), [Table 156](#), [Table 157](#), and [Table 158](#).

The distribution of the maximum severity of symptoms of each ARI/AFI event by baseline flavivirus status and treatment group will be presented in [Table 161](#), [Table 162](#), [Table 163](#), [Table 164](#), and [Table 165](#), as well as by infection confirmation status in [Table 168](#), [Table 169](#), [Table 170](#), [Table 171](#), and [Table 172](#). For subjects reporting at least one AFI/ARI the duration of reported symptoms will be described in [Table 175](#), [Table 176](#), [Table 177](#), [Table 178](#), [Table 179](#), and by infection confirmation status in [Table 182](#), [Table 183](#), [Table 184](#), [Table 185](#), and [Table 186](#).

Individual subject listings of AFI/ARI data will be included in [Listing 12](#) (subject information), [Listing 13](#) (medical treatment sought for ARI/AI), [Listing 14](#) (ARI/AI symptoms), [Listing 15](#) (vital signs), and [Listing 16](#) (laboratory results).

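### AFI/ARI has no exception for Days 1-8 after a dose, so a solicited rash away from the injection site, or a qualifying fever, is also counted as surveillance illness by treatment group

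*SAP*

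**What the plan says.** SAP 3.3 defines both illnesses by symptoms. For rash: "Acute rash illness (ARI) is defined as any new rash not limited to vaccination site". For fever: "Acute febrile illness (AFI) is defined as grade 1 or higher fever on at least 2 consecutive days accompanied by any of the following", the accompanying signs being new rash beyond the vaccination site, arthralgia or nonpurulent conjunctivitis. Neither definition has a time limit relative to a dose or requires that a vaccine reaction be ruled out, and ARI has no minimum grade.

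Collection is continuous. Protocol 9.4 states: "AFI and ARI will be collected after signing ICF through the end of the study". SAP 4.5 likewise observes subjects "from the time of signing the informed consent form through follow-up". The question is put in the days just after vaccination. The Day 2 visit (Protocol 8.2.2) instructs: "Ask about febrile/rash illness. If the subject reports history of AFI/ARI within the past 14 days", and a febrile/rash assessment follows. The same question is asked at the Day 4 and Day 8 contacts and at all three matching contacts after the second dose.

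The solicited systemic reactions in Protocol 7.1.2, collected through Day 8 after each dose, begin with fever and include "arthralgia (joint pain exclusive of the injection site), headache, rash, nausea, vomiting, diarrhea, and abdominal pain". The grading table in Protocol 9.2.2 (SAP Table 4) restricts solicited rash and arthralgia to those not at the injection site.

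On reporting, SAP 9.9 says: "The percentage of subjects who develop ARI or AFI will be summarized by treatment group and baseline flavivirus status". The Table 140 shell counts subjects with at least one AFI/ARI event over the Safety population of the group, without requiring laboratory confirmation.

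**The concern.** Protocol 11.1 gives the purpose of the surveillance: "to obtain preliminary data on the incidence and clinical presentation of naturally occurring flavivirus infections after vaccination". A rash or short fever caused by the injection is not such an infection, yet under these definitions it is reported twice: once as reactogenicity and once as AFI/ARI.

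The two kinds of event need not be distributed alike across arms. Natural infection strikes vaccine and placebo recipients according to exposure. Reactogenicity may be more frequent after alum-adjuvanted ZPIV than after saline. A difference between columns in the all-event AFI/ARI tables could then reflect reactogenicity and be read as a difference in illness, which is a sensitive comparison for a flavivirus vaccine in an endemic area. Subjects whose only episode is a reaction would also enter the severity and duration tables, where N is limited to subjects with at least one AFI/ARI.

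**Working it through.** **1. Overlap of definitions.**

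| Event on Days 1-8 after a dose | Solicited reaction? | AFI/ARI? |
|---|---|---|
| New rash away from the injection site, any grade | Yes | Yes (ARI) |
| Fever of 38.0°C or more on 2 consecutive days, with arthralgia or such a rash | Yes | Yes (AFI) |
| Fever on one day only, without rash | Yes | No |
| Arthralgia without fever or rash | Yes | No |
| Headache, fatigue, myalgia, nausea and the rest, alone | Yes | No |

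The overlap is complete for new solicited rash, conditional for fever, and absent for the other reactions taken alone.

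**2. Where the events go.** They enter Tables 140-146 (events, medication, medical care), 161-167 (severity) and 175-181 (duration), all by treatment group. An unconfirmed reaction also enters the negative-confirmation rows of Tables 147-153, 154-160, 168-174 and 182-188. Tables 154-160 express results as a percentage of all AFI/ARI events, so a reaction enlarges that denominator too. No summary table separates early episodes. Listing 12 gives illness start, associated dose and days post dose by subject.

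**3. Share of follow-up.** The affected tables run through 12 months after the final vaccination, that is, to about Day 388. Two windows of 8 days: 2 × 8 = 16; 16/388 = 4.1%.

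**4. Size.** The plan gives no rate for rash, so it has no figure of its own to reproduce here. The nearest is the chance of at least one event among 80 ZPIV recipients at a true rate of 2.0%, stated in SAP Table 8 as 80.1%. The formula 1 − (1 − p)^n gives 1 − 0.98^80 = 80.1%, so it reproduces.

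For illustration only, assume a vaccine-caused rash away from the site with probability r per dose, independent over two doses. The per-subject probability is q = 1 − (1 − r)²; the expected number among 80 (45 + 35, SAP 4.4.3) is 80q; the chance of at least one is 1 − (1 − q)^80.

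| r (assumed) | q | Expected among 80 | Chance of at least one |
|---|---|---|---|
| 1% | 1.99% | 1.6 | 80% |
| 2% | 3.96% | 3.2 | 96% |
| 3% | 5.91% | 4.7 | 99% |
| 5% | 9.75% | 7.8 | >99% |

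If none of these subjects had another episode, the ZPIV percentage in Table 140 would rise by q, about 2 to 10 points over this range. A rate near zero is equally compatible with the documents and would add almost nothing.

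**5. Placebo comparison.** With 5 + 5 = 10 placebo recipients, 0/10 has an exact 95% upper limit of 1 − 0.025^(1/10) = 30.8%.

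**6. Why the titre route needs care for early episodes.** Serum for humoral immunity is drawn before dosing on Day 1 and Day 29, and on Days 15 and 43 (SAP 4.5). An illness visit soon after dose 1 is bracketed by Days 1 and 15, and one soon after dose 2 by Days 29 and 43. In each pair a dose lies between the samples, so a 4-fold ZIKV rise may be the intended vaccine response.

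**The case against.** The strongest reply is that the affected rows are not endpoints. The exploratory objective concerns ZIKV and DENV infections, and both exploratory endpoints require evidence of infection. The all-event tables sit under other safety measures, where counting every cause is defensible, and the plan repeats the summaries by confirmation status. In a trial of about 90 subjects, Listing 12 lets a reader find early episodes one by one. No test is planned for AFI/ARI, and ten placebo recipients support little inference.

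That stands, and it makes this a matter of presentation. It does not remove the mixing: the by-arm all-event tables, the negative-confirmation rows and the event denominator of Tables 154-160 still combine reactions with illness, and no summary row shows how many.

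Three stronger readings are tempting but unsupported.

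- A reader might infer that a large share of ZPIV AFI/ARI will be reactogenicity. The documents give neither a rash rate nor a background AFI/ARI rate. The common reactions that Protocol 2.3.1 lists for related inactivated vaccines do not include rash, which appears there only as a sign of very rare serious allergic reactions.
- A reader might infer that severity and duration are necessarily diluted. These tables take each subject's maximum over episodes, so a mild reaction does not mask a worse illness in the same subject. The effect is limited to subjects whose only episode is a reaction.
- A reader might infer that the infection endpoints are contaminated throughout. An unconfirmed reaction does not enter them. The opening is the ZIKV titre route when a dose falls between the paired samples.

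**Conclusion.** The overlap is established from the text alone: the definitions, collection period and visit prompts include Days 1-8 after each dose, and no summary table separates the two kinds of event. Its consequence is limited to descriptive AFI/ARI tables by arm and the negative-confirmation rows and event denominators. The primary safety endpoints are unaffected.

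The size cannot be given. The windows cover about 4% of follow-up in these tables, but solicited reactions fall in them by definition. The illustrative 1.6 to 7.8 subjects among 80 rest on an assumed rash rate of 1% to 5% per dose, independence between doses, and no allowance for the AFI route. That the effect differs between ZPIV and saline is plausible, not shown. The point merits a small change before the final tables are produced because the remedy is cheap and the by-arm comparison is easily misread.

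**What to change.** In SAP 9.9, leave the AFI/ARI definition and all collection unchanged and do the following:

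1. Derive a flag for AFI/ARI with onset on Days 1-8 after either dose, counting the day of dosing as Day 1.
2. Keep the all-event row. Add one row for episodes with onset inside the window and one for those outside it, in the incidence, severity and duration tables. Footnote that a subject with both kinds of episode appears in both rows.
3. State that surveillance illness by arm is read from the outside-window row plus any early episode confirmed by PCR or by a 4-fold DENV titre rise. Keeping the DENV titre route matters because SAP 3.3 accepts it, and a PCR-only rule would drop such infections.
4. State that a ZIKV titre rise alone does not place an early episode with surveillance illness when a study dose lies between the paired samples.

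The cost is one derived variable, from dates already planned for Listing 12, and a few extra rows per table. A few true early illnesses without qualifying confirmation will appear in the inside-window row; they remain visible there and in the all-event row.

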4.5. Immunogenicity and Safety Variables

In general, multiple observations within a specific visit period were accepted. In the case of multiple observations within a specific window, the assessment value closest to the scheduled visit date will be used in the analyses for the post-baseline records. If observations have the same distance to the scheduled assessment, the latest one will be used. Unless otherwise specified, the last assessment value recorded prior to the prime dose will be used as baseline. All the recorded data will be listed. Samples from days on which a subject was vaccinated were collected prior to vaccination.

All subjects were to have venous blood samples for assessment of humoral immunity collected on Days 1, 15, 29, 43, 57, 209, 388, and 569. Assay results are reported as the ZIKV titers giving 50% reduction in viral infection (MN50) and IgG ELISA titers. DENV neutralization titers were also to be recorded in subjects reporting ARI or AFI. Samples from the immunogenicity visits immediately before and after the illness visit were used to measure DENV titers, which will be used to aid laboratory confirmation of ZIKV/DENV infection.

Solicited adverse events were collected from the time of study vaccine administration through Day 8 after each dose. Subjects received a memory aid to record any solicited AEs on each day. The following injection site reactogenicity events were measured and grading according to the scale in [Table 3](#) and [Table 4](#): pain, tenderness, pruritis, ecchymosis, erythema, and induration. The following systemic solicited events were measured and graded according to the scale in [Table 4](#) and [Table 5](#): feverishness, fatigue, malaise, myalgia, arthralgia, headache, nausea, vomiting, diarrhea, abdominal pain, rash, and fever.

Vital signs of heart rate and blood pressure were measured in subjects at Days 1, 2, 8, 15, 29, 30, 36, 43, and 57. The measurements were assessed for adverse events of bradycardia/tachycardia and systolic and diastolic hypotension/hypertension according to the scale in [Table 6](#).

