	Baseline ZIKV Seronegative and DENV Seropositive												
	Baseline ZIKV Seronegative and DENV Seronegative												
Repeat Day 29 for:													
Day 57 (28 Days Post-Dose 2)													
Day 209 (180 Days Post-Dose 2)													
Day 750 (721 Days Post-Dose 2)													
Peak Post-Baseline													

Table 26: ZIKV Microneutralization Antibody (MN50) Seroconversion Results with 95% Confidence Intervals by Time Point, Treatment Group, and Baseline Flavivirus Immune Status -- Immunogenicity Population (continued)

Seroconversion is defined as at least a 4-fold rise in ZIKV MN50 titers from baseline.

N* = Number of subjects with results available at baseline and the specified time point

n = number of subjects seroconverting at the specified time point

95% CI = 95% confidence interval.

Table with similar format:

Table 27: ZIKV Microneutralization Antibody (MN50) Seroconversion Results with 95% Confidence Intervals by Time Point, Treatment Group, and Baseline Flavivirus Immune Status – Per Protocol Population

ZIKV ELISA Titers

Tables with format similar to Table 20:

Table 28: ZIKV ELISA Geometric Mean Titer (GMT) Results with 95% Confidence Intervals by Time Point, Treatment Group, and Baseline Flavivirus Immune Status – Immunogenicity Population

Table 29: ZIKV ELISA Geometric Mean Titer (GMT) Results with 95% Confidence Intervals by Time Point, Treatment Group, and Baseline Flavivirus Immune Status – Per Protocol Population

Table 30: ZIKV ELISA Geometric Mean Fold Rise (GMFR) Results with 95% Confidence Intervals by Time Point, Treatment Group, and Baseline Flavivirus Immune Status – Immunogenicity Population

[Implementation Note: Baseline results are not included in this table.]

Table 31: ZIKV ELISA Geometric Mean Fold Rise (GMFR) Results with 95% Confidence Intervals by Time Point, Treatment Group, and Baseline Flavivirus Immune Status – Per Protocol Population

[Implementation Note: Baseline results are not included in this table.]

Tables with format similar to Table 24:

Table 32: ZIKV ELISA Seropositivity Results with 95% Confidence Intervals by Time Point, Treatment Group, and Baseline Flavivirus Immune Status – Immunogenicity Population

[Implementation note: seropositivity is defined as titers ≥ 200 and ≥ 600 .]

Table 33: ZIKV ELISA Seropositivity Results with 95% Confidence Intervals by Time Point, Treatment Group, and Baseline Flavivirus Immune Status – Per Protocol Population

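### The confirmed-infection rule has no exception for a study dose given between the two sera, so a ZPIV response plus a rash can be counted as titre-confirmed infection (exploratory endpoint 2)

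*SAP*

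**What the plan says.** SAP 3.3 gives two alternative routes to laboratory confirmation in a subject with AFI or ARI: PCR within 14 days of onset, or "a 4-fold rise in DENV or ZIKV neutralization titers between samples collected at the last visit prior to and at the first visit following" the illness visit. Either one suffices, so a negative PCR does not block the titre route. The same 4-fold rule, with no condition on dosing, appears in the Protocol Summary, Protocol 3.2.3, SAP 3.2, SAP 9.9 and the footnotes to SAP Tables 147, 154, 168 and 182.

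The clinical trigger is light: "Acute rash illness (ARI) is defined as any new rash not limited to vaccination site". Surveillance covers the vaccination period, because SAP 4.5 follows AFI/ARI and "all related adverse events from the time of signing the informed consent form through follow-up".

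On sampling, SAP 4.5 has sera for "assessment of humoral immunity collected on Days 1, 15, 29, 43, 57, 209, 388, and 569", and "Samples from days on which a subject was vaccinated were collected prior to vaccination". Doses are given on Days 1 and 29 (SAP 4.4.5). SAP 15 says that ZIKV and DENV MN50 are run on the samples nearest the illness visit on each side, where possible.

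The vaccine-response endpoint uses the same fold rise: "Seroconversion is defined as at least a 4-fold rise in ZIKV MN50 titers from baseline" (Table 26 footnote). Protocol 2.2 expects two 5 mcg doses to produce moderate ZIKV neutralizing titres.

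**The concern.** A paired-serum rise shows infection only if nothing else given between the two samples can produce it. Here an immunogen designed to produce exactly that rise can fall between them. Rash is also a solicited systemic reaction, graded only when it is away from the injection site (SAP Table 4), so a reactogenicity rash can meet the ARI definition. Solicited fever lasting two days with arthralgia could likewise meet AFI.

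Saline cannot cause this error, so it runs in one direction. It adds apparent infections to the ZPIV arms, in a trial that follows subjects for 24 months partly to describe natural flavivirus infection after vaccination (Protocol 2.2). What is at stake is a misclassified case in small descriptive counts, together with its severity and duration.

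**Working it through.** **Fold-rise criterion.** SAP 3.3 works one example: a titre below the LLOQ is reported as 5, and seroconversion then needs at least 4 × 5 = 20, which reproduces. A subject going from 5 before the illness visit to 20 after it also meets the titre route to confirmed infection.

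**Which illness visits span a dose.** Inputs: sera at Visit 00 and Days 1, 15, 29, 43, 57; dose-day sera pre-dose; doses on Days 1 and 29. Take the last serum strictly before the visit and the first strictly after. A dose on day d lies inside the pair if prior serum day ≤ d < following serum day.

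| Illness visit (nominal day) | Serum before | Serum after | Dose between | Affected days |
|---|---|---|---|---|
| 1 | Visit 00 | 15 | Day 1 | 1 |
| 2–14 | 1 | 15 | Day 1 | 13 |
| 15 | 1 | 29 | Day 1 | 1 |
| 16–28 | 15 | 29 | none | 0 |
| 29 | 15 | 43 | Day 29 | 1 |
| 30–42 | 29 | 43 | Day 29 | 13 |
| 43 | 29 | 57 | Day 29 | 1 |
| 44–56 | 43 | 57 | none | 0 |

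Total: 1 + 13 + 1 + 1 + 13 + 1 = 30 days.

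**Sensitivity to conventions.**
- Same-day serum counted as the after sample: Days 2–15 and 30–43, 28 days. Counted as the before sample: Days 1–14 and 29–42, 28 days. With the illness visit as anchor, 30 − 4 = 26 days (2–14 and 30–42) are affected however a same-day serum is treated.
- Anchor: SAP 3.3 uses the illness visit, Protocol 3.2.3 and SAP 3.2 use the AFI/ARI itself, and SAP 9.9 uses illness onset. Onset on Day 27 seen on Day 31 gives Days 29/43 by visit (spans a dose) but Days 15/29 by onset (does not). Onset on Day 10 seen on Day 20 gives Days 15/29 by visit (does not) but Days 1/15 by onset (does). The anchor changes which cases are affected; it does not remove the problem.
- The MN50 shells (Tables 20, 24, 26) have no Day 15 or Day 43 rows. If only the shell time points had results, the span would be Days 1–57. SAP 15 points to the nearest samples instead, so 30 days is the working figure.

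**Effect of one misclassified subject on Table 147** (denominator: Safety population in the column; planned numbers 35, 45 and 10, total 90).
- 2.5 mcg: 1/35 = 2.9% (exact 95% CI 0.07–14.9%).
- 5 mcg: 1/45 = 2.2% (0.06–11.8%).
- All Subjects: 1/90 = 1.1%.
- Placebo: 0.

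The titre-rise row and the any-positive row each gain the case, and the negative row loses it. The PCR row does not change. Tables with confirmation rows are 147–160, 168–174 and 182–188: 14 + 7 + 7 = 28. Tables 154–160 use the number of AFI/ARI events as denominator, which is not known in advance.

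**The case against.** The case for leaving the rule alone is reasonable. The endpoint is exploratory and descriptive, and no primary or secondary endpoint, hypothesis test or halting rule uses it. With about 10 placebo recipients, no difference between arms could be established anyway. PCR confirmation has its own row, and Listing 12 shows virus, sample days and days since dose, so any case can be traced. Fever or acute illness can defer a dose (Protocol 5.2 and 9.5.2), which thins the Day 1 and Day 29 edges. All of this stands and sets the severity. It does not correct the summary rows, because Listing 12 carries no rule.

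A reader might infer something stronger: that the Day 1/Day 15 pair is the seroconversion comparison itself, so one result would be reported both as vaccine response and as infection. The documents do not establish this. Secondary endpoint 1 is "Frequency of seroconversion to ZIKV at each post-vaccination visit measured by ZIKV ELISA and neutralization assay in comparison with baseline samples", and the parenthesis that follows names Visit 00. SAP 4.5 says that "the last assessment value recorded prior to the prime dose will be used as baseline", but only unless otherwise specified. That conflict is unresolved, and the Table 26 shell has no Day 15 row. What is shared is the 4-fold criterion, not a proven identity of comparison.

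A reader might also take the distortion to be confined to the ZPIV columns. It also reaches All Subjects.

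**Conclusion.** The concern holds as a minor point. Applied as written, the rule can label an intended vaccine response as confirmed infection for illness visits on nominal Days 1–15 and 29–43. This can happen in ZPIV recipients and not in saline recipients. One case is worth 2.9% or 2.2% of a ZPIV column in Table 147 and about 1.1% of All Subjects.

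This rests on nominal visit days, both sera being available, and the illness-visit anchor of SAP 3.3. Actual windows move with visit windows, a postponed boost or a lost sample; 11 Group 1 subjects lost samples at time points that SAP 5 does not name. The number of cases cannot be derived, because the documents give neither an illness-visit rate in these windows nor a 4-fold response rate after one dose, so none is claimed.

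**What to change.** Add to SAP 3.3, for all arms: *A ZIKV titre rise without a positive ZIKV PCR is classed as indeterminate, not confirmed, when a study vaccination falls between the two sera used.* State one anchor, illness visit or onset, for choosing the sera, and use it in SAP 3.2, 3.3 and 9.9. Add an Indeterminate row, separate from the negative row, in Tables 147–160, 168–174 and 182–188; align the footnotes; and carry the status into Listings 13–16 and 22. Flag by footnote any DENV-only rise across a dose, since the documents do not establish that ZPIV leaves DENV titres unchanged. Separate ZIKV and DENV rows are optional.

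The cost is one sentence, one anchor statement, one row and footnote edits in 28 shells, and one more status value in five listings. No new data are needed, because Listing 12 already holds them. Under the working pairing, affected visit-days fall from 30 to 0. The downside is that a true PCR-negative ZIKV infection in these windows is reported as indeterminate. Visits on Days 16–28 and 44–56 have no dose between their sera and stay under the current rule, although a post-dose titre may still be rising there; excluding them is at most an optional sensitivity analysis.
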